7. NON-SAFETY SECONDARY ENDPOINTS

7.1. HOSPITALIZATION

Objective: To test whether HCQ or HCQ + azithromycin has an effect on the duration of hospitalization among persons who become hospitalized with COVID-19 disease compared to control.

Outcome: Days of hospitalization

Cohort: ITT Cohort

Data sets: Hospitalized Data Set

Endpoint: Number of days from admission to discharge (this may be informatively censored by death)

Analysis details:

Because of very low incidence of hospitalization in this study, only the minimum, median and maximum of days of hospitalization will be reported by arm.

7.2. DISEASE SEVERITY

Objective: To test whether HCQ or HCQ + azithromycin has an effect on disease severity compared to placebo

Outcomes: Disease severity is measured using two scales: the WHO Ordinal Scale for Clinical Improvement and The Modified Flu-PRO

Cohort: ITT Cohort

Data sets:

Endpoints: This analysis will have two endpoints: 1) the WHO Ordinal Scale for Clinical Improvement measured on days 14, 21 and 28 and 2) the score from the modified Flu-PRO measured daily on the first 14 days in the study, excluding the baseline (day 1). The modified Flu-PRO score is calculated as the mean score across the Flu-PRO questionnaire (sum numeric value over all symptoms and divided by number of symptoms[1]).

Analysis details: The distribution of scores will be described by arm at each visit including minimum, maximum, median and IQR. Boxplots of the Flu-PRO score will be presented by visit and arm and further stratified by risk cohort.

Testing: Because the maximum observed value may have undesirable statistical properties, we will perform hypothesis testing on all the observed data over the first 14 days. Mixed effects models with random slopes and intercepts will be used to model the mean Flu-PRO score over time with a main effect of randomization. The interaction between randomization and time will also be included to explore the potential effect of randomization on the change in Flu-PRO score over time. Testing between arms will be based on the coefficients from the main treatment effect and the interaction term using Wald tests. These tests will detect average differences between the arms in Flu-PRO scores. Recognizing that linear models may not well fit the Flu-PRO trajectories, an exploratory model using B-splines will also be fit.

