10.1.2. Participant Survey

Participants will be asked to complete surveys (Daily Surveys and Exit Contact Survey) that will include questions about symptoms from both the drug regimen and respiratory and systemic

symptom, review of concomitant medications, and other pertinent topics. A modified self-reported Flu-Pro instrument will be completed each day through Day 14 and on Day 21 and Day 28 to assess degree of illness (Yu 2020) (Appendix 12).

10.2. *Adverse Events*

Participants will be asked to complete surveys (Daily Surveys and Exit Contact Survey) that include information on any symptoms that they are experiencing. In addition, AE review by a staff member (via telephone, Telehealth, or text messaging) will be performed.

All AEs must be recorded on the electronic case report forms (eCRFs) if any of the following criteria have been met:

- All AEs meeting SAE definition
- All AEs leading to discontinuation of study medication
- All AEs judged by the site Investigator to be associated with study medication

10.2.1. *Adverse Events*

An AE is any untoward medical occurrence that occurs in a patient or clinical investigation subject administered a pharmaceutical product, which does not necessarily have to have a causal relationship with this treatment. An AE can therefore be any unfavorable and unintended sign (including abnormal laboratory findings), symptom, or disease temporally associated with the use of an investigational product, whether or not considered related to the product.

AEs may include the onset of new illness and the exacerbation of pre-existing medical conditions. An AE can include an undesirable medical condition occurring at any time, including baseline or washout periods, even if no study treatment has been administered.

10.2.2. *Serious Adverse Events*

An SAE is defined as any untoward medical occurrence that:

- Results in death
- Is life-threatening
- Requires inpatient hospitalization or prolongation of existing hospitalization
- Results in persistent or significant disability/incapacity
- Is an important medical event that may not be immediately life-threatening or result in death or hospitalization but may jeopardize the participant or may require intervention to prevent one of the other outcomes listed in the definition above

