2.1. BASELINE DATA

The following baseline variables will be described: age, sex, presence of known COVID-19 risk factors (includes all factors that categorize participants into the high-risk category), race/ethnicity and time since onset of symptoms.

Baseline variables will be summarized overall and within high and low risk strata by treatment arm. Because of the potential for imbalance between arms due to household-based randomization, statistical testing across arms will be performed using gee adjusted by risk strata with exchangeable correlation within household. If there appears to be imbalance across the arms, ($p<0.10$), the variable will be adjusted for in primary analyses.

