4. EFFICACY/EFFECTIVENESS ANALYSES

4.1. EFFICACY ANALYSES

All efficacy analyses will be adjusted for age, sex at birth and time from symptom onset to enrollment. These adjustments will be additive unless otherwise specified.

All analyses will account for the household clustering using robust standard errors as available. If not available, bootstrap methods will be used.

For time to event analyses, baseline (time 0) will be day of the enrollment visit.

Endpoints will be summarized as number of participants: hospitalized without prior LRTI, hospitalized with prior LRTI, died without prior LRTI, died with prior LRTI, who meet LRTI definition. These will be shown as counts and percentages overall and by cohorts defined in Section 2.2 within further breakdown by arm.

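### The Flu-PRO severity model does not use the Day 1 score as a baseline covariate, which costs precision and leaves chance Day 1 imbalance in a secondary comparison

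*SAP*

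**What the plan says.** SAP 7.2 replaces the protocol's peak Flu-PRO score with "the score from the modified Flu-PRO measured daily on the first 14 days in the study, excluding the baseline (day 1". Mixed models with random intercepts and slopes are to "model the mean Flu-PRO score over time with a main effect of randomization". The section adds: "The interaction between randomization and time will also be included". On inference it says: "Testing between arms will be based on the coefficients from the main treatment effect and the interaction term using Wald tests". A B-spline version is exploratory. The cohort is ITT. No Day 1 term is listed.

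Three other places might have supplied one:

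- SAP 4.1: "All efficacy analyses will be adjusted for age, sex at birth and time from symptom onset to enrollment". SAP 7.2 does not say whether this carries over; I assume that it does.
- SAP 2.1: "The following baseline variables will be described: age, sex, presence of known COVID-19 risk factors", followed by race/ethnicity and time since symptom onset. Flu-PRO is not on the list. For a listed variable that looks imbalanced (p<0.10), "the variable will be adjusted for in primary analyses"; Flu-PRO severity is a secondary endpoint.
- Protocol 11.3.1 names age, BMI and days of symptoms as covariates for the primary analyses, with precision as the reason.

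The score is scheduled for Day 1 in the Schedule of Activities, Protocol 9.1 and Appendix 12. Protocol 10.1.2 says that a "modified self-reported Flu-Pro instrument will be completed each day through Day 14".

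**The concern.** The baseline value of a repeatedly measured outcome is usually among its better predictors. Arm is constant within a person, so differences in severity at entry stay in the variance of the arm comparison unless the model accounts for them. Any chance difference between arms on Day 1 also carries into the follow-up comparison in proportion to r.

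The plan's own reasoning points the same way. Protocol 11.3.1 adjusts for baseline variables to gain precision, and SAP 2.1 expects that household randomization may leave the arms unbalanced. Enrollment was stopped early (SAP 5), so precision is likely to be scarce. What is at stake is the sharpness of one secondary comparison and how it reads if the arms happen to differ on Day 1.

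**Working it through.** **No stated figure to reproduce.** The documents give no SD, target difference, power or Day 1 to follow-up correlation for Flu-PRO.

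**Inputs.** From the SAP: outcome days 2-14, alpha 0.05 (taken as two-sided), and 165 per arm. The last is the initial target in SAP 1.5.1 for other endpoints and serves only as a scale, because enrollment stopped early and the achieved number is not given. Assumed: r, the correlation of the Day 1 score with the Days 2-14 mean after the existing covariates, over 0.2 to 0.7.

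**1. Mean arm difference.** The variance with the Day 1 score in the model is (1 − r²) times the variance without it. The equivalent gain in sample is 1/(1 − r²) − 1. An effect with 80% power unadjusted has power Φ[(1.96 + 0.84)/√(1 − r²) − 1.96] after adjustment.

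| r (assumed) | 1 − r² | Variance cut | Equivalent extra sample | n per arm matching 165 unadjusted | Power, from 80% |
|---|---|---|---|---|---|
| 0.2 | 0.96 | 4% | 4% | 159 | 82% |
| 0.3 | 0.91 | 9% | 10% | 151 | 84% |
| 0.4 | 0.84 | 16% | 19% | 139 | 86% |
| 0.5 | 0.75 | 25% | 33% | 124 | 90% |
| 0.6 | 0.64 | 36% | 56% | 106 | 94% |
| 0.7 | 0.51 | 49% | 96% | 85 | 98% |

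**2. The coefficients that SAP 7.2 tests.** The formula above is for the mean difference. With an interaction in the model, the arm main effect is the fitted arm difference at time zero, and SAP 7.2 does not state the time origin. I computed generalized least squares variances for a random-intercept and slope model, before and after conditioning on Day 1. That conditioning is equivalent to adding Day 1 and Day 1-by-time. Time zero was Day 1.

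| Assumed intercept variance, slope variance, covariance, residual variance | r | Ratio, mean difference | Ratio, arm effect at time zero | Ratio, arm-by-time |
|---|---|---|---|---|
| 0.15, 0.0008, −0.008, 0.20 | 0.52 | 0.73 | 0.71 | 0.90 |
| 0.20, 0.001, −0.008, 0.10 | 0.69 | 0.52 | 0.43 | 0.86 |

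Over five assumed settings (r from 0.52 to 0.88) the arm-by-time ratio was 0.79 to 0.97. With complete, balanced data a Day 1 main effect alone leaves the arm-by-time variance unchanged (ratio 1.00), because a term constant over time explains none of the variation in slopes.

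**3. Simulation.** In 4,000 trials per setting with 165 per arm, comparing Days 2-14 means, the variance ratio was 0.74 at r = 0.52 and 0.54 at r = 0.69. Type I error for these two settings was 4.7% and 4.9% unadjusted, and 5.0% and 5.6% adjusted. The unadjusted test is therefore valid on average.

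**4. Chance imbalance.** The SD of the standardized Day 1 difference is √(2/n), ignoring household clustering:

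- 165 per arm: √(2/165) = 0.11, so P(|difference| > 0.2 SD) is 7%.
- 75 per arm (assumed): √(2/75) = 0.16, so P(|difference| > 0.2 SD) is 22%.

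A Day 1 difference of d SD shifts the unadjusted statistic by r·d/√(2/n) standard errors. With r = 0.5, d = 0.2 and n = 165, the shift is 0.5 × 0.2/0.110 = 0.91. The type I error given that imbalance is 1 − Φ[(1.96 − 0.91)/0.866] + Φ[(−1.96 − 0.91)/0.866], about 11%. With d = 0.1 it is 4.4%, below nominal. The excess and the shortfall average out over randomizations.

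**The case against.** The strongest reply is that the planned analysis is already valid. Randomization protects the unadjusted test, and the simulation shows error near 5% either way. A reader might infer that the estimate is biased, or that removing Day 1 from the outcome is itself a mistake. The documents support neither: a score labelled baseline does not belong in a post-baseline outcome unless it is modelled as such.

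A reader might also take the gain as free and available for everyone. It is not. SAP 7.2 uses the ITT cohort, while SAP 2.2 defines mITT by completion of the Day 1 questionnaire, so some ITT participants may lack a score. A plain covariate would drop them. Nor is it certain that the score is taken before dosing. Protocol 9.1 and Appendix 12 list the survey ahead of the medication, but the same Day 1 survey asks about dosing adherence. Flu-PRO includes nausea, vomiting and diarrhea, which Protocol 7.2.1 lists as HCQ effects.

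The size is uncertain too. The relevant r is what remains after age, sex and symptom time, and at r = 0.2 the gain is small. All of this stands, and it limits the claim and enlarges the fix.

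Two defences do not remove the point. Random intercepts model within-person correlation but do not take severity at entry out of the arm comparison. The summaries and boxplots by visit in SAP 7.2 may show a Day 1 imbalance but do not correct for it.

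**Conclusion.** The omission is clear from the text: no section puts Day 1 Flu-PRO into the severity model. The consequence is a loss of efficiency and of balance given the arms actually drawn, not bias and not an inflated overall error rate.

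The variance reduction of 4% to 49% applies to the mean arm difference for an assumed r of 0.2 to 0.7; it should not be read as the gain for both planned Wald tests. The arm main effect gains a similar amount or more if time is counted from Day 1. The interaction gains less, and only if Day 1-by-time is included. Confidence is high in the omission and moderate at best in the size. The change is worth making, but the stakes are modest: one secondary endpoint in the SAP for the HCQ arms, whose enrollment was stopped for operational futility.

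**What to change.** In SAP 7.2, adopt one of two forms:

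1. **Covariate form.** Add Day 1 Flu-PRO and Day 1-by-time as fixed effects in both the linear and B-spline models. State a missing-baseline rule that loses no ITT participant, for example simple imputation of the Day 1 score without reference to arm.
2. **Response form.** Keep Day 1 as a response with a mean common to all arms, and let arm terms act only from Day 2. Participants without a Day 1 score then stay in the analysis.

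Under either form, state the time origin, so that it is clear at which day the arm main effect is evaluated, and say whether the SAP 4.1 covariates apply. Confirm that the Day 1 survey was completed before the first dose. A score recorded after dosing should be handled under the missing-baseline rule, or omitted as a baseline response. If results by arm have already been seen, report the adjusted model as a labelled supplementary analysis.

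The cost is one or two model terms and a few sentences. No new data collection is needed.

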11.3.2.2. Disease Severity

Disease severity, as measured by the WHO Ordinal Scale for Clinical Improvement ([Appendix 11](#)), will be compared between the groups using a proportional odds model.

Disease severity over the first 14 days and at Days 21 and 28 will also be measured by the modified Flu-PRO survey ([Appendix 12](#)). Results will be analyzed as for the WHO Ordinal Scale for Clinical Improvement.

Progression and regression of disease severity will be modeled using multistate models.

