1.3. UPDATED OBJECTIVES AND ENDPOINTS

The trial was stopped early due to operational futility to meet the first two primary objectives (development of LRTI and hospitalization/death). In light of this several of the secondary endpoints have been updated as follows.

- Because of the very few number of hospitalizations, the Secondary Objective 2 will no longer be evaluated.
- The endpoint for Secondary Objective 3 will be the Flu-PRO score evaluated daily over 14 days instead of only the maximum value. Appropriate statistical methods will be detailed in Section 7.2.
- The CDC definition of COVID-19 will now define the endpoint for Secondary Objective (SO) 4. The endpoints currently presented in Table 1 for SO 4 will be summarized over time as described in Section 7.2.

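### SAP 7.2 lists the WHO Ordinal Scale as a severity endpoint under an objective of testing, but specifies no formal comparison of the arms on it and does not say that it is descriptive only

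*SAP*

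**What the plan says.** SAP 7.2 states its purpose as a test: "Objective: To test whether HCQ or HCQ + azithromycin has an effect on disease severity compared to placebo". It then names the endpoints: "This analysis will have two endpoints: 1) the WHO Ordinal Scale for Clinical Improvement measured on days 14, 21 and 28", and second the daily modified Flu-PRO score over the first 14 days, excluding Day 1. The cohort is ITT.

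The descriptive part covers both scales: "The distribution of scores will be described by arm at each visit including minimum, maximum, median and IQR". Boxplots are added for Flu-PRO only. The testing part says "we will perform hypothesis testing on all the observed data over the first 14 days", and the method is given for Flu-PRO alone: "Mixed effects models with random slopes and intercepts will be used to model the mean Flu-PRO score over time", with a treatment-by-time interaction, Wald tests and an exploratory B-spline version.

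Protocol 11.3.2.2 says that severity on the WHO scale "will be compared between the groups using a proportional odds model". SAP Table 1 lists the peak WHO score under Secondary Objective 3 for the HCQ arms. SAP 1.3 announces one change to that objective: "The endpoint for Secondary Objective 3 will be the Flu-PRO score evaluated daily over 14 days instead of only the maximum value". It does not mention the WHO scale.

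**The concern.** One of the two severity endpoints has an objective of testing but no analysis that could meet it. If the SAP is followed literally, the report will show by-arm summaries of the WHO scale with no measure of the difference between arms or of its uncertainty.

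The summaries chosen suit this scale poorly. In Protocol Appendix 11, scores 3 and above mean hospitalized or dead, and SAP 1.3 notes that hospitalizations were very few. Most participants should therefore score 0, 1 or 2, and a median on so few values barely moves.

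Because the SAP neither specifies a test nor rules one out, the decision whether to test the scale, and how, is also left open until after the data are seen.

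**Working it through.** **Step 1. The passages side by side.** The plan gives no figure for this point, so the first check is textual.

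| Item | WHO Ordinal Scale | Modified Flu-PRO |
|---|---|---|
| Named as endpoint in SAP 7.2 | Yes, Days 14, 21, 28 | Yes, daily to Day 14 |
| By-arm summaries in SAP 7.2 | Yes | Yes, plus boxplots |
| Model, estimate or test in the SAP | None | Mixed model, Wald tests, exploratory splines |
| Analysis in Protocol 11.3.2.2 | Proportional odds model | Same as the WHO scale |
| Change declared in SAP 1.3 | None | Peak replaced by daily score |

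Days 21 and 28 fall outside the 14-day testing window. Day 14 falls inside it, but the only model given is for mean Flu-PRO. No other SAP section models the WHO scale.

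**Step 2. Was it dropped on purpose?** Where the SAP gives up a test, it says so with a reason. SAP 1.3 states that Secondary Objective 2 will not be evaluated because hospitalizations were so few, and SAP 7.1 limits that outcome to descriptive values for the same reason. There is no such statement for the WHO scale. The reason given in 7.2, that a maximum may behave badly statistically, could explain leaving the peak score. It does not explain leaving the scores at fixed days untested.

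**Step 3. What the planned summaries can show.** The documents give no WHO score distribution, so three Day 14 control distributions over scores 0 / 1 / 2 / 3+ are assumed. With a common odds ratio of 0.5 favouring active, the odds of scoring at or below each cut double: active cumulative share = 2o / (1 + 2o), where o = c / (1 − c) and c is the control share.

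| Assumed control (%) | Score 0: control → active | Score ≤1: control → active | Median in both arms |
|---|---|---|---|
| 10 / 55 / 33 / 2 | 10% → 18.2% | 65% → 78.8% | 1 |
| 5 / 70 / 23 / 2 | 5% → 9.5% | 75% → 85.7% | 1 |
| 20 / 65 / 13 / 2 | 20% → 33.3% | 85% → 91.9% | 1 |

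Worked example for row 1, score ≤1: o = 0.65 / 0.35 = 1.857; 2o = 3.714; 3.714 / 4.714 = 78.8%.

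The median is 1 in both arms in every row. The quartiles behave differently. In row 1 the upper quartile moves from 2 to 1, because the share at ≤1 passes 75%. In row 3 the lower quartile moves from 1 to 0, because the share at 0 passes 25%. In row 2 the control share at ≤1 is exactly 75%, so a sample upper quartile lands on either side almost by coin toss. With no effect, two such arms differ in about 2 × 0.5 × 0.5 = 50% of trials.

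**Step 4. Simulation.** Each setting used 2000 replicates and a Wilcoxon rank-sum test at two-sided 5%, which is the proportional odds score test without covariates. The ranges run over the three distributions. 165 per arm is the target in SAP 1.5.1; 75 per arm is an assumption made because enrolment stopped early.

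| Quantity | OR 0.5 | OR 0.6 | No effect |
|---|---|---|---|
| Arm medians identical | about 99% or more | – | – |
| At least one quartile differs (75 and 165 per arm) | about 48–94% | about 49–84% | about 1–58% |
| Rank-test power, 165 per arm | about 79–88% | about 53–68% | – |
| Rank-test power, 75 per arm | about 44–58% | about 26–35% | – |

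Simulation error on a power near 80% is √(0.8 × 0.2 / 2000) ≈ 0.9 percentage points.

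**The case against.** The strongest reply is that the change was deliberate. SAP 1.3 speaks of a single endpoint for Secondary Objective 3, the Flu-PRO score, in the context of early stopping, and another sparse secondary endpoint was reduced to description. On that reading the WHO scale was demoted. This is plausible, but SAP 7.2 still lists two endpoints under an objective of testing. The two sections conflict, and neither states a demotion.

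Four stronger readings might be inferred, and the documents do not support them:

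- **That the arms are never compared on this scale.** By-arm summaries are planned at each visit. What is missing is a formal comparison. SAP 4.1.2 also applies Fisher's exact test to COVID-19 hospitalization or death by Day 28, which broadly matches scores 3 to 8. That covers only the high-risk mITT cohort and does not reach the difference between scores 1 and 2.
- **That the IQR would hide a real shift.** Under the assumptions above it often moves. The difficulty is that it also moves often by chance.
- **That the severity objective goes unanswered.** It gets formal tests on daily Flu-PRO. The gap concerns the WHO scale alone.
- **That the SAP removed an analysis the protocol had fixed for the HCQ arms.** The supplied protocol is the LPV/r amendment. Its 11.3.2.2 is not arm-specific, and SAP Table 1 carries the WHO scale for the HCQ arms, but the model wording in force for those arms cannot be checked. The protocol's endpoint is also the peak score, with no analysis day named, so day-specific models would not simply reinstate it.

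**Conclusion.** The point holds as a gap in a secondary analysis. SAP 7.2 names the WHO scale as an endpoint to be tested and gives it no estimate, interval or test, and no section says that this is intended. The primary endpoints are unaffected.

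The textual finding rests on no assumption. The size does: the three score distributions, the odds ratios and 75 per arm are all assumed. The simulation covers Day 14 only and ignores household clustering and covariates. Part of its power comes from the boundary between scores 0 and 1, where score 0 requires no clinical or virological evidence of infection, and not only from limitation of activities. Given early stopping, the lower power range is the more relevant one. An added test would therefore serve mainly to provide an interpretable estimate with its uncertainty, and a non-significant result would not show absence of effect.

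**What to change.** In SAP 7.2, add a proportional odds model of the WHO score for each active arm against control, with Day 14 as the main time point and Days 21 and 28 as supportive. Adjust for risk cohort and the SAP 4.1 covariates (age, sex at birth, time from symptom onset to enrollment), with household-robust standard errors. Report the common odds ratio with its 95% confidence interval and the count in each category by arm, alongside the summaries already planned.

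Reconcile SAP 1.3 with 7.2 so that both name the same endpoints for Secondary Objective 3. If the sponsor intends description only, both sections should say so and give the reason.

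The cost is a few sentences and a standard model on data already scheduled for collection. The downside is up to 2 active arms × 3 days = 6 further secondary comparisons of modest power. Naming Day 14 as the main time point leaves two main comparisons, one per active arm.
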